1.2 Purpose

[figure not shown]
This trial is designed to answer the question whether the combination of Secukinumab with lifestyle intervention can primarily improve skin symptoms and secondly cardiometabolic status more than Secukinumab alone in psoriasis patients with concomitant metabolic syndrome by dual targeting of the shared pathophysiology behind both diseases, which is systemic inflammation.

2 Study objectives and endpoints

Table 2-1 Objectives and related endpoints

| Objective(s) | Endpoint(s) |
|---|---|
| Primary Objective(s) | Endpoint(s) for primary objective(s) |
| 
 To demonstrate that the combination of Secukinumab (300 mg, 4-weekly s.c.) with lifestyle intervention results in higher psoriasis treatment efficacy than Secukinumab alone in psoriasis patients with concomitant metabolic syndrome | 
 Percentage of patients achieving PASI90 at week 28 in both randomized treatment arms, Secukinumab alone and Secukinumab combined with lifestyle intervention |
| Secondary Objective(s) | Endpoint(s) for secondary objective(s) |
| 
 To explore treatment efficacy of Secukinumab (300 mg, 4-weekly s.c.) combined with lifestyle intervention in comparison to Secukinumab alone To evaluate the effect of Secukinumab (300 mg, 4-weekly s.c.) combined with lifestyle intervention in comparison to Secukinumab alone on systemic inflammation To evaluate the effect of Secukinumab (300 mg, 4-weekly s.c.) combined with lifestyle intervention in comparison to Secukinumab alone on glucose metabolism To evaluate the effect of Secukinumab (300 mg, 4-weekly s.c.) combined with lifestyle intervention in comparison to Secukinumab alone on lipid metabolism To evaluate the effect of Secukinumab (300 mg, 4-weekly s.c.) combined with lifestyle intervention in comparison to Secukinumab alone on body weight and waist circumference To evaluate the effect of Secukinumab (300 mg, 4-weekly s.c.) combined with lifestyle intervention in comparison to Secukinumab alone on systolic and diastolic blood pressure To evaluate the effect of Secukinumab (300 mg, 4-weekly s.c.) combined with | 
 PASI75, 90 and 100 as well as absolute PASI scores in both treatment arms at week 1, 2, 3, 4, 8, 12, 16, 20, 24 and 28 hsCRP in both treatment arms throughout the duration of the core study HbA1c, fructosamine and fasting plasma glucose in both treatment arms throughout the duration of the core study Total cholesterol, LDL, HDL and triglycerides in both treatment arms throughout the duration of the core study Waist circumference, body weight and BMI in both treatment arms throughout the duration of the core study Systolic and diastolic blood pressure in both treatment arms throughout the duration of the core study Absolute DLQI, relative change of DLQI, proportion of patients with |

| Objective(s) | Endpoint(s) |
|--|---|
| lifestyle intervention in comparison to Secukinumab alone on health-related quality of life, itch, pain and scaling as well as mental well-being | DLQI 0/1, absolute WHO-5, relative change in WHO-5, absolute self-assessed itch, pain, scaling, relative change in self-assessed itch, pain, scaling in both treatment arms throughout the duration of the core study |

| Objective(s) | Endpoint(s) |
|---|---|
| 
 To explore the effect of Secukinumab (300 mg, 4-weekly s.c.) combined with lifestyle intervention in comparison to Secukinumab alone on biomarkers including but not limited to those linked to lipid, glucose, muscle and bone metabolism, liver fibrosis/steatosis, heart injury, as well as to inflammatory processes in a subgroup of 100 patients (50 treated with secukinumab and lifestyle intervention and 50 treated with secukinumab alone) | 
 At baseline (week 0), week 16 and week 28 the following markers will be assessed: Free fatty acid serum profile, sThy-1, adiponectin, leptin, insulin, HOMA-IR, proinsulin, IL-6, TNF-alpha, M30 assay, IL-1 beta, IL-1Ra, IL-18, IL-18bp, P1NP, CTX, RANKL, OPG, sclerostin, NT-proBNP, CD154, and a 30-panel multiplex inflammatory cytokine and chemokines panel |

3 Investigational plan

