5.6.5 Early study termination by the sponsor

The study can be terminated by Novartis at any time for any reason. This may include reasons related to the benefit risk assessment of participating in the study, practical reasons, or for regulatory or medical reasons (including slow enrolment). Should this be necessary, the patient must be seen as soon as possible and treated as a prematurely withdrawn patient. The investigator may be informed of additional procedures to be followed in order to ensure that adequate consideration is given to the protection of the patient's interests. The investigator will be responsible for informing the Institutional Review Board/Independent Ethics Committee (IRBs/IECs) of the early termination of the trial.

6 Visit schedule and assessments

Table 6-1 lists all of the assessments and indicates with an "x" when the visits are performed.

Patients should be seen for all study visits on the designated day, or as close to it as possible. Recommended study visit windows are +/- 2 days for visits 2 – 6, +/- 5 days for visits 7 – 12 and +/- 7 days for visits E1 – E3. The same visit windows are recommended for the lifestyle intervention visits associated to the study visits.

Missed or rescheduled visits should not lead to automatic discontinuation. Patients who prematurely discontinue the study for any reason should be scheduled for a visit as soon as possible, at which time all of the assessments listed for the final visit will be performed. In case of premature discontinuation during the core study the final visit is the week 28 visit, in the case of premature discontinuation during the extension period the final visit is the week 56 visit. At this final visit, all dispensed investigational product should be reconciled and the adverse event and concomitant medications reconciled on the CRF.

Table 6-1 lists assessments that are recorded in the clinical database (marked “X” if entered via the eCRF or “C” if entered centrally, e.g. via a central laboratory) and assessments that are source documentation only (marked “S”). Assessments that are source documentation only will not be entered into the eCRF.

If for any reason the subject is a screen failure, the subject may be re-screened. There is no restriction on the number of times a potential subject may be re-screened or on how much time must pass from the date of screen failure and the date of re-screening.

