If a subject re-screens for the study, then the subject must sign a new ICF and be issued a new subject number prior to any screening assessment being conducted for the subject under the new screening subject number. For all subjects, the investigator/qualified site staff will record if the subject was re-screened on the re-screening eCRF and any applicable screening numbers the subject was issued prior to the current screening number. The date of the new informed consent signature must be entered on the Informed Consent eCRF to correspond to the new screening subject number. For re-screening, all screening assessments must be performed per protocol, except for the tuberculosis (TB) work up if applicable, if performed not more than 12 weeks before randomization.

Table 6-1 Assessment schedule

| Visit Number | 1 | 2 | 3 | 4 | 5 | 6 | 7 | 8 | 9 | 10 | 11 | 12 | E1 | E2 | E3 | US V ⁴ |
|--|-------------|---|---|----|----|----|----|----|-----|-----|-----|-----|-----|-----|-----|-------------------|
| Week | -4 - -1 | 0 | 1 | 2 | 3 | 4 | 8 | 12 | 16 | 20 | 24 | 28 | 36 | 44 | 56 | |
| Day | -28 - -7 | 1 | 8 | 15 | 22 | 29 | 57 | 85 | 113 | 141 | 169 | 197 | 253 | 309 | 393 | |
| Obtain informed consent | X | | | | | | | | | | | | | | | |
| Obtain informed consent for biomarker sub-study ⁹ | X | | | | | | | | | | | | | | | |
| Demographics | X | | | | | | | | | | | | | | | |
| Inclusion/exclusion criteria ¹ | X | X | | | | | | | | | | | | | | |
| Smoking history | X | | | | | | | | | | | X | | | X | |
| Medical history and prior medications | X | | | | | | | | | | | | | | | |
| Cardiovascular/metabolic medical history | X | | | | | | | | | | | | | | | |
| Concomitant medications | X | X | X | X | X | X | X | X | X | X | X | X | X | X | X | X |
| Physical examination | S | S | | | | | | | S | | | S | | | S | S ⁵ |
| Height | X | | | | | | | | | | | | | | | |
| Weight | X | X | X | X | X | X | X | X | X | X | X | X | X | X | X | X ⁵ |
| Vital signs | X | X | X | X | X | X | X | X | X | X | X | X | X | X | X | X ⁵ |
| Waist and hip circumference | X | X | X | X | X | X | X | X | X | X | X | X | X | X | X | |
| Routine Laboratory [‡] | C | C | | C | | C | C | C | C | C | C | C | C | C | C | C ⁵ |
| Fasting Laboratory [‡] | C | C | | | | | C | | C | | | C | C | C | C | C ⁵ |
| QuantIFERON test ² | C | | | | | | | | | | | | | | | C ⁵ |
| Serum pregnancy test ³ | C | | | | | | | | | | | C | | | C | C ⁵ |
| Local pregnancy test | | X | | | | | | | | | | | | | | C ⁵ |

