2.6.2 Handling of missing values/censoring/discontinuations

Non-responder imputation will also be applied to all secondary response variables. For continuous secondary endpoints, all available measurements will be included in the Mixed Model for Repeated Measures (MMRM).

[REDACTED]

[REDACTED]

[REDACTED]

[REDACTED]

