5.5 Visit windows and mapping of visits

Visit-windows will be used for safety & efficacy data that is summarized by visit; they are based on the study assessment schedule and comprise a set of days around the nominal visit day. For any assessment there will be a visit window to cover the complete range of days within the study. The analysis visit will be used for listing of visit and period. If a visit falls after the last visit window it is not assigned an analysis visit and will be listed under label “After Week 56”

Table 5-1 Assessment windows for scheduled visits

Analysis Visit	Week	Scheduled Day	Visit Window
Baseline	BSL	1	-28 days to Day 1
Week 1	1	8	Day 2-11
Week 2	2	15	Day 12-18
Week 3	3	22	Day 19-25
Week 4	4	29	Day 26-43
Week 8	8	57	Day 44-71
Week 12	12	85	Day 72-88
Week 16	16	113	Day 89-127
Week 20	20	141	Day 128-155
Week 24	24	169	Day 156-183
Week 28	28	197	Day 184-211
Week 36 (E1)	36	253	Day 212-295
Week 44 (E2)	44	309	Day 296-379
Week 56 (E3)	56	393	Day 380-435

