5.5.1 Multiple assessments within visit-windows

When there are multiple assessments in a particular visit-window, the following rules are applied to select one value “representing” the patient in summary statistics in a visit-window. The baseline value is represented by the last observation prior to the first dose unless otherwise specified.

For baseline assessment definition see [Section 2.1.1.2](#).

For post-baseline visit-windows the following applies (unless otherwise specified):

- for quantitative variables, the closest to the actual visit is chosen (if two assessments have the same distance, then the earlier one will be chosen);
- for qualitative variables, the worst record is selected. It is noted that in the analyses performed, worst case is always well defined.
- in case qualitative variables are based on quantitative variables, e.g. PASI 75 response, the visit will be assigned to the quantitative variable, and this visit will be used for the derived qualitative variable.

6 Reference

Al-Mutairi N, Nour T (2014) The effect of weight reduction on treatment outcomes in obese patients with psoriasis on biologic therapy: a randomized controlled prospective trial. Expert Opin Biol Ther; 2014;14:749-56

Finlay AY and Khan GK (1994) Dermatology Life Quality Index (DLQI): A simple practical measure for routine clinical use. Clin Exp Dermatol; 19: 210-216.

Clinical Development

CAIN457A/METABOLYX

CAIN457ADE08

A randomized, multicenter 28 week study to compare the efficacy and safety of combining Cosentyx (Secukinumab) (4-weekly, 300 mg s.c.) with a lifestyle intervention to Cosentyx therapy alone in adult patients with moderate to severe plaque-type psoriasis and concomitant metabolic syndrome, followed by a 28 week extension period

Biomarker Sub-study Statistical Analysis Plan (SAP)

Author:	
Document type:	SAP Documentation (Biomarker sub-study)

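### Core SAP Table 5-1 ends the Week 12 window at Day 88, so Week 12 visits on Days 89-90, which the protocol treats as on schedule, are filed as Week 16 and Week 12 is left empty

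*Protocol*

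**What the plan says.** Protocol section 2, Table 2-1, lists PASI 75, 90 and 100 together with "absolute PASI scores in both treatment arms at week 1, 2, 3, 4, 8, 12, 16, 20, 24 and 28" as secondary endpoints, so Week 12 and Week 16 are separate time points. Core SAP section 2.6.1 plans an analysis at each of them, with odds ratios and p-values for the responder endpoints.

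Protocol section 6, Table 6-1, schedules Weeks 8 to 28 on Days "57 | 85 | 113 | 141 | 169 | 197". Visit 8 (Week 12) is therefore Day 85 and Visit 9 (Week 16) is Day 113. The text before the table recommends a tolerance of plus or minus "5 days for visits 7 – 12".

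Core SAP section 5.5 states: "Visit-windows will be used for safety & efficacy data that is summarized by visit". Its Table 5-1 assigns Days 72-88 to Week 12 and Days 89-127 to Week 16.

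Where a window holds several assessments, core SAP section 5.5.1 keeps one: "for quantitative variables, the closest to the actual visit is chosen". Derived responses follow the score they come from: "in case qualitative variables are based on quantitative variables, e.g. PASI 75 response, the visit will be assigned to the quantitative variable".

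For missing data, core SAP section 2.6.2 states: "Non-responder imputation will also be applied to all secondary response variables". Continuous endpoints enter the MMRM with whatever measurements are available.

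**The concern.** The Week 12 window runs 13 days before its scheduled day but only 3 days after it. The Week 16 window runs 24 days before and 14 days after. Neither core SAP section 5.5 nor the list of changes in core SAP section 4 gives a reason for this asymmetry.

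Because the late side is shorter than the protocol's own tolerance, a patient seen on schedule for Week 12 can have no Week 12 record in the analysis. For a responder endpoint that is more than a lost value: a response that was observed is reported as a non-response. Late make-up visits face the same problem. Protocol section 5.5.4 allows one skipped visit with home dosing between Weeks 8 and 24, followed by a visit at which the missed assessments are done. A Week 12 make-up visit after Day 88 is also filed as Week 16.

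At stake are the Week 12 results for skin response, quality of life, weight, waist, blood pressure and the routine laboratory markers taken at Visit 8. To a lesser degree the Week 16 results are at stake too, where a Week 12 value stands in for a missed Week 16 visit.

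**Working it through.** **Inputs.** Scheduled days and tolerances come from Protocol section 6 and Table 6-1. Windows come from core SAP Table 5-1. The selection and imputation rules come from core SAP sections 5.5.1 and 2.6.2.

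**Step 1: the rule behind the table.** Upper bound = (scheduled day + next scheduled day) / 2, rounded down.

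| Week | Midpoint | Rounded down | SAP upper bound |
|---|---|---|---|
| 1 | (8+15)/2 = 11.5 | 11 | 11 |
| 2 | (15+22)/2 = 18.5 | 18 | 18 |
| 3 | (22+29)/2 = 25.5 | 25 | 25 |
| 4 | (29+57)/2 = 43 | 43 | 43 |
| 8 | (57+85)/2 = 71 | 71 | 71 |
| **12** | **(85+113)/2 = 99** | **99** | **88** |
| 16 | (113+141)/2 = 127 | 127 | 127 |
| 20 | (141+169)/2 = 155 | 155 | 155 |
| 24 | (169+197)/2 = 183 | 183 | 183 |

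The rule reproduces eight of the nine bounds exactly and fails only at Week 12. Week 28 and the extension rows are built differently.

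**Step 2: comparison with the protocol tolerance.** Visit 8: 85 - 5 = 80 and 85 + 5 = 90, so Days 80-90, which is 11 days. Days 89 and 90 lie outside the SAP window, so 2/11 = 18% of the recommended days are misfiled. The same check on every post-baseline row finds no other window that fails to contain its protocol tolerance. For the primary endpoint, Week 28 is Days 184-211 and contains Days 192-202.

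**Step 3: what happens to a Day 89 or 90 record.** I read the closest-record rule as distance from the scheduled day. The distance to Day 113 is 24 days (Day 89) or 23 days (Day 90). An on-schedule Week 16 visit is at most 5 days from Day 113.
- If the Week 16 visit took place within its window, that record is selected and the Week 12 record is not used.
- If the Week 16 visit was missed, the Week 12 value is reported as Week 16.
- In both cases Week 12 is empty. Table 6-1 plans no PASI at unscheduled visits, so nothing else would normally fill it.

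**Step 4: size.** Let f be the share of patients whose Week 12 visit falls on Day 89 or 90. The documents do not give f. If visit days are normal around Day 85 and truncated at 5 days either side, an SD of 1 day gives almost none, and SDs of 2, 3 and 4 days give 3.7%, 9.5% and 12.8%. An even spread gives 18%. If response is unrelated to visit day, the reported rate = true rate × (1 - f). For illustration I borrow the protocol's Week 28 planning rates (81% and 90%) as true Week 12 rates and take all 760 patients as attending:

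| f | Patients (760 × f) | 81% reported as | 90% reported as | Difference (9 points) becomes |
|---|---|---|---|---|
| 0% | 0 | 81.0% | 90.0% | 9.0 |
| 2% | 15 | 79.4% | 88.2% | 8.8 |
| 5% | 38 | 77.0% | 85.5% | 8.6 |
| 10% | 76 | 72.9% | 81.0% | 8.1 |
| 18% (2/11) | 138 | 66.3% | 73.6% | 7.4 |

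The difference column is 9 × (1 - f) and assumes the same f in both arms. Visits after Day 90 would add to f.

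**The case against.** The strongest reply is that the loss may be trivial. Protocol section 6 asks sites to see patients on the designated day or as near to it as possible, and the 5 days are a recommendation. If sites comply closely, almost no visit reaches Day 89. This stands: the 18% needs an even spread that runs against that instruction, and the lower end of the range is close to zero.

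A second reply is that section 5.5.1 selects a value for summary statistics, while section 2.6.2 puts all available measurements into the MMRM. That leaves some doubt about whether the unselected record is dropped from the model. It does not restore Week 12, because under the windows the record is labelled Week 16.

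A third is that Week 12 is one of ten PASI time points under an objective worded as exploratory, and that both arms follow the same rule. That is correct and limits the consequence.

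A reader might also infer more than the documents support:
- **A visible dip in response between Week 8 and Week 16.** The documents give no response rates for those weeks, and a loss of a few percent need not produce a dip on a rising curve.
- **Every Day 89-90 record is thrown away.** It is displaced only if a closer record exists in the Week 16 window.
- **All Week 12 endpoints are scored as failures.** Non-response scoring applies to the responder endpoints only. Absolute PASI and the other continuous endpoints have a missing Week 12 value.
- **The biomarker SAP has the same error.** Its Week 16 window starts at Day 99 and that sub-study samples only at Weeks 0, 16 and 28, so it has no Week 12 sample to misfile.

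**Conclusion.** The window is wrong as written. Week 12 is the only boundary from Week 1 to Week 24 that departs from the midpoint, and the only post-baseline window that does not contain the protocol's own tolerance. Applied literally, the SAP's rules score a patient who responded at an on-schedule Day 89 or 90 visit as a Week 12 non-responder.

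The size is unknown. Between about 0% and 18% of Week 12 records are affected, depending entirely on an assumed visit-day distribution, plus any make-up visits after Day 90. Week 12 response rates are understated in both arms in proportion. With the same visit timing in both arms, the difference between arms shrinks by the same factor. The documents give no reason to expect timing to differ by arm, so they do not support a claim of bias towards either one. The primary analysis is untouched. The point should be corrected, but it does not threaten the trial's main conclusion.

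**What to change.** In core SAP section 5.5, Table 5-1, set Week 12 to Days 72-99 and Week 16 to Days 100-127. This is the table's own convention: a day equidistant from two visits, such as Day 71 or Day 127, goes to the earlier one. Ending Week 12 at Day 98 and starting Week 16 at Day 99 is equally acceptable and matches the biomarker SAP. Either choice contains the whole of Days 80-90. The biomarker SAP needs no change.

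The cost is two numbers in one table, with no new data. If the core analysis has already been produced, rerun the Week 12 and Week 16 results under the corrected windows. That includes the Week 16 weight-loss subgroup analyses in core SAP section 2.8. Report how many records changed window, by arm, which would also replace the assumed range with an actual figure.

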2.5.3 Handling of missing values/censoring/discontinuations

Patients who do not have a valid PASI assessment at week 28 will be regarded as non-responders for the primary analysis.

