2.7.5 Effect of Secukinumab combined with lifestyle intervention on a biomarker sub-study

A biomarker sub-study will be performed during the core study to explore the effect of Secukinumab (300 mg, 4-weekly s.c.) combined with lifestyle intervention in comparison to Secukinumab alone on biomarkers in a subgroup of 100 patients (50 treated with secukinumab and lifestyle intervention and 50 treated with Secukinumab alone).

At baseline (week 0), week 16 and week 28 the following markers will be assessed using fasting blood samples: Free fatty acid serum profile, sThy-1, adiponectin, leptin, insulin, HOMA-IR, proinsulin, IL-6, TNF-alpha, M30 assay, IL-1 beta, IL-1Ra, IL-18, IL-18bp, P1NP, CTX, RANKL, OPG, sclerostin, NT-proBNP, CD154, and a 30-panel multiplex inflammatory cytokine and chemokines panel. All endpoints of the biomarker sub-study will be summarized by visit and analyzed using the same MMRM model as described in [section 2.6.1](#).

Only patients participating in the biomarker sub-study will be considered for this analysis. As the biomarker sub-study is planned to be conducted for the biomarkers samples collected under fasting conditions, so the subjects with non-fasting status will be analysed separately and independently.

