5.2 Visit windows and mapping of visits

Visit-windows will be used for biomarker sub-study data that is summarized by visit; they are based on the study assessment schedule and comprise a set of days around the nominal visit day. For any assessment there will be a visit window to cover the complete range of days within the study. So, the overlapping visit window period will be used for the analyses, as mentioned below in [Table 5-1](#).

Table 5-1 Assessment windows for scheduled visits

Analysis Visit	Week	Scheduled Day	Visit Window
Baseline	0	1	-28 days to Day 1
Week 16	16	113	Day 99-127
Week 28	28	197	Day 183-225

Clinical Development

CAIN457A/METABOLYX

CAIN457ADE08

A randomized, multicenter 28 week study to compare the efficacy and safety of combining Cosentyx (Secukinumab) (4 weekly, 300 mg s.c.) with a lifestyle intervention to Cosentyx therapy alone in adult patients with moderate to severe plaque type psoriasis and concomitant metabolic syndrome, followed by a 28 week extension period

Extension Period Statistical Analysis Plan (SAP)

Document type:	SAP Documentation
Document status:	Addendum 1.0
Release date:	19-Sep-2022
Number of pages:	21

Property of Novartis
Confidential
May not be used, divulged, published or otherwise disclosed
without the consent of Novartis

Template Version 4.0, Effective from 23-Apr-2021

Document History – Changes compared to previous final version of SAP

Date	Time point	Reason for update	Outcome for update	Section and title impacted (Current)
27-Jul-2022	Prior to DB lock	Creation of final version	N/A - First version	NA
19-Sep-2022	After Final DB lock	Creation of Addendum version 1.0	Text modified in section 2.6.1	2.6.1

Table of contents

Table of contents	3
List of abbreviations	5
1 Introduction	6
1.1 Study design.....	6
1.2 Study objectives and endpoints	7
2 Statistical methods.....	8
2.1 Data analysis general information	8
2.1.1 General definitions	8
2.2 Analysis sets	8
2.3 Patient disposition, demographics, and other characteristics	8
2.3.1 Patient disposition	8
2.3.2 Demographics and other characteristics.....	9
2.4 Treatments (study treatment, rescue medication, concomitant therapies, compliance).....	9
2.4.1 Study treatment / compliance.....	9
2.4.2 Study Compliance	9
2.4.3 Concomitant and post therapies	10
2.5 Analysis supporting study objective(s).....	10
2.5.1 Endpoint(s).....	10
2.5.2 Statistical hypothesis, model, and method of analysis.....	11

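### Core SAP Table 5-1 files a Visit 12 PASI done on Day 212–224 under Week 36, which can turn an observed response into an imputed failure; the core and biomarker SAPs also use different windows for the same markers

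*Protocol*

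**What the plan says.** The primary endpoint in Protocol Section 2 (Table 2-1) is "Percentage of patients achieving PASI90 at week 28 in both randomized treatment arms". For the sub-study the same table says "At baseline (week 0), week 16 and week 28 the following markers will be assessed"; it names time points and gives no windows. Protocol Table 6-1 places the PASI and the Week 28 sub-study sample at the same Visit 12 (Day 197). The margin recommended for that visit in Protocol Section 6 is plus or minus "5 days for visits 7 – 12".

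Core SAP Section 5.5 states: "Visit-windows will be used for safety & efficacy data that is summarized by visit". Its Table 5-1 sets Week 28 at Day 184–211, Week 36 at Day 212–295, Week 44 at Day 296–379 and Week 56 at Day 380–435. Extension SAP Table 6-1 repeats the last three rows. Under core SAP Section 5.5.1, where a window holds several quantitative values, the one closest to the visit is kept. For a response derived from a score, "the visit will be assigned to the quantitative variable, and this visit will be used for the derived qualitative variable". Section 2.5.3 adds: "Patients who do not have a valid PASI assessment at week 28 will be regarded as non-responders for the primary analysis".

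For the markers, core SAP Section 2.7.5 says: "All endpoints of the biomarker sub-study will be summarized by visit and analyzed using the same MMRM model". The biomarker SAP analyses them again and has its own table in Section 5.2: "Visit-windows will be used for biomarker sub-study data that is summarized by visit". There Week 16 is Day 99–127 and Week 28 is Day 183–225. Core Table 5-1 has Week 16 at Day 89–127.

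**The concern.** A window table should send an assessment to the visit it belongs to, or at least to the nearest one. Core Table 5-1 does this for most of the core study and stops doing so at the boundary that matters most, the end of Week 28. Combined with non-responder imputation, a clear PASI90 response seen at a late Visit 12 could enter the primary analysis as a failure. Equal losses in both arms shrink the difference and cost power. Unequal losses bias it, and the trial is open label. The later boundaries misplace extension visits in the same way.

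For the markers the problem is different: one blood sample can be Week 28 in one SAP and Week 24 or Week 36 in the other, so two planned analyses of the same marker could give different Week 28 results.

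**Working it through.** **1. Boundaries.** The scheduled days in core Table 5-1 are 29, 57, 85, 113, 141, 169, 197, 253, 309 and 393. Midpoint = (earlier day + later day) / 2.

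| Boundary | Midpoint | Last day in core SAP | Agrees |
|---|---|---|---|
| Week 4/8 | 43 | 43 | yes |
| Week 8/12 | 71 | 71 | yes |
| Week 12/16 | 99 | 88 | no |
| Week 16/20 | 127 | 127 | yes |
| Week 20/24 | 155 | 155 | yes |
| Week 24/28 | 183 | 183 | yes |
| Week 28/36 | 225 | 211 | no |
| Week 36/44 | 281 | 295 | no |
| Week 44/56 | 351 | 379 | no |

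**2. Distances, as days to the earlier and the later visit.**
- Week 28/36: Day 212 is 15 and 41; Day 224 is 27 and 29; Day 225 is 28 and 28. Days 212–224 are nearer Week 28 but filed as Week 36. Day 225 is equidistant.
- Week 36/44: Day 282 is 29 and 27; Day 295 is 42 and 14. Days 282–295 are nearer Week 44 but filed as Week 36.
- Week 44/56: Day 352 is 43 and 41; Day 379 is 70 and 14. Days 352–379 are nearer Week 56 but filed as Week 44.

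**3. Path to the primary endpoint.** Suppose Visit 12 takes place on Day 215. Table 5-1 labels its PASI Week 36. If E1 takes place near Day 253, Section 5.5.1 keeps the E1 value for Week 36, so the Visit 12 score is not used. With no other PASI on Day 184–211 there is no Week 28 value, and Section 2.5.3 makes the patient a non-responder. No step uses the biomarker SAP.

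**4. The plan's own sample size.** Inputs (Protocol Section 9.8): 81% against 90%, two-sided 5%, 90% power, 1:1. The pooled two-proportion formula gives 320 per arm; with continuity correction it gives 342, the plan's figure. The matching power formula is

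Φ[(d − 1/n − 1.96·s0) / s1], with s0 = √(2·p̄(1 − p̄)/n) and s1 = √((a(1 − a) + b(1 − b))/n).

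At n = 342, d = 0.09, s0 = 0.0269 and s1 = 0.0267, this is Φ(1.28) = 90.1%. For a 7.5-point effect it gives 74.7%. The plan states 90% and 75%.

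**5. Sensitivity.** Let a share m of patients in each arm be lost to the window and counted as failures. The rates become 0.81(1 − m) and 0.90(1 − m). With n = 380 per arm:

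| Assumed m | Response rates | Power |
|---|---|---|
| 0% | 81.0% / 90.0% | 93.0% |
| 1% | 80.2% / 89.1% | 91.3% |
| 3% | 78.6% / 87.3% | 87.5% |
| 5% | 77.0% / 85.5% | 83.4% |

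If 2% were lost in the combination arm only, power would be 75.6%. If 2% were lost in the control arm only, the rejection probability would be 97.9%; that rise is bias, not information.

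**6. Markers.** Every marker listed in biomarker SAP Section 2.5.1 is also in core SAP Section 2.7.5. A sample on Day 89–98 is Week 16 in the core SAP and in no window of the biomarker SAP. Day 183 is Week 24 against Week 28. Days 212–225 are Week 36 against Week 28. In total 15 days are classed differently for Week 28 and 10 for Week 16.

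**The case against.** The core Week 28 window is defensible on its face. It runs from −13 to +14 days, like Weeks 20 and 24, and is far wider than the recommended margin (Day 192–202); Day 212–225 lies 10 to 23 days beyond that margin. The SAP nowhere states a midpoint rule, and for visits 28 days apart a fixed 14-day limit gives the same boundaries. That stands as an explanation of Day 211. It does not explain a Week 36 row that reaches back 41 days, or a Week 44 row that reaches forward 70.

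A later PASI may also measure something else. After Week 28 psoriasis therapy is free and arm A may start the lifestyle programme (Protocol Section 3.1). Day 225 is 56 days after the nominal last dose on Day 169. This stands, and it rules out simply widening the window for every PASI.

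The SAP does not define a valid Week 28 PASI, and its windows are stated for data summarised by visit. It is therefore open whether the window or the nominal Visit 12 decides the primary endpoint. This stands too: the misclassification is conditional on the first reading.

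The documents do not show that late visits are common. The deviation list (core SAP Section 5.4) has COVID-19 codes for missed visits, visits away from the site and changed assessments, none of which is a visit moved to a later date.

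Finally, the sub-study has no Week 24 or Week 36 sample, so wider biomarker windows are reasonable in themselves. That does not justify analysing the same markers under other windows in the core SAP.

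**Conclusion.** The point holds as two separate defects of wording. First, the core SAP sends Days 212–224 to the more distant visit. Read with its response and imputation rules, it can replace an observed Visit 12 response by a failure when no PASI lies on Day 184–211. Second, the core and biomarker SAPs classify the same samples differently at Weeks 16 and 28.

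A reader might infer that the conflict between the SAPs causes the primary-endpoint failures, or that every patient with a PASI on Day 212–225 becomes a non-responder. The documents support neither. The biomarker windows apply only to sub-study data and never to PASI, so the outcome would be the same without that SAP. A patient who also has a PASI on Day 184–211 keeps a Week 28 value.

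The size is unknown. The fall in power from 93% to between 91% and 83% rests on an assumed 1% to 5% of patients affected equally in both arms and responding like the others. It also takes 81% and 90% as the rates after all other imputation, and uses a simple two-proportion test instead of the planned logistic model. The sample size itself reproduces and is not in question.

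**What to change.** - State that the valid Week 28 PASI is the actual Visit 12 assessment, including one on Day 212–225 if it precedes any extension-period psoriasis therapy or arm A lifestyle intervention. Such a value then no longer counts as Week 36. Keep Day 184 as the lower limit, because Protocol Section 6 has patients who leave the core study early undergo the Week 28 assessments ahead of time.
- Report by arm how many patients enter on a Day 212–225 PASI, and give the primary result under the strict Day 184–211 window as a sensitivity analysis.
- Use one set of Week 16 and Week 28 windows for the markers in the core and biomarker SAPs.
- Set the Week 36/44 and Week 44/56 boundaries at Day 281 and Day 351 in core Table 5-1 and extension Table 6-1.

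The cost is SAP wording and one extra table. The downside is that a few Week 28 values will lie up to 56 days after the nominal last dose (225 − 169). If outcome data have already been analysed, label the change post hoc and show both results.
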